## Statistical Analysis Plan (SAP)

---

Total. The number of AEs and the number and percentage of subjects that experienced the given AE will be summarized by the above mentioned treatment groupings.

The three AE summaries will consist of:

- Overall Summary of Adverse Events within First 45 Days of Initial Administration of IP
- Adverse Events within First 45 Days of Initial Administration of IP by System Organ Class, Preferred Term, and Maximum Severity
- Adverse Events within First 45 Days of Initial Administration of IP by System Organ Class, Preferred Term, and Closest Relationship to Study Medication

Unless otherwise specified, at each level of subject summarization of AEs, a subject will be counted once, even if they reported more than one event. If more than one occurrence of an event is reported, the event of the worst severity or the worst-case relationship assessment will be summarized. In summaries by SOC and PT, adverse events will be sorted in descending frequency by SOC and PTs within each SOC according to the total number of events among all subjects.

All AE summaries will be presented for the Safety population.

### 9.10.2 Primary Endpoint 1b – Physical Examination, Vital Signs, ECG, & Laboratory Results, Cohorts 1-4

To further evaluate primary objective #1, to evaluate the safety and tolerability of repeat intramuscular (IM) administration of G03-52-01 in healthy adult subjects, primary endpoint #1b will be used:

The occurrence of changes from baseline in PE, vital signs, and clinical safety laboratory values following administration of G03-52-01 to the final follow-up visit

Clinical laboratory parameters for chemistry, hematology, urine dipstick, and urine toxicology will be summarized in tables and listed, using System International (SI) units where applicable. In table summaries, continuous parameters will be evaluated using descriptive statistics [number of subjects (n), mean, SD, median, first quartile, third quartile, minimum, and maximum] at each time point and each change from baseline to follow-up time point. Categorical parameters will be summarized using counts and percentages and shifts from baseline will be separately summarized. Shift tables will include both the shift from baseline to each post-baseline visit as well as the maximum shift from baseline. If a lab value is reported using a non-numeric qualifier [e.g., less than (<) a certain value, or greater than (>) a certain value], then the given numeric value will be used in the summary statistics, and the nonnumeric qualifier will be dismissed; however, results with non-numeric qualifiers will be listed as-is in the listings. Laboratory parameters will be listed by subject at each time point, which will display the result, change from baseline (if applicable), the normal range for the parameter, and whether the result was clinically significant (either clinically low or clinically high). For the urine dipstick laboratory assessment, if any of the parameter results are abnormal (>+1), then a complete urinalysis will be performed and presented in a separate subject listing.

## Statistical Analysis Plan (SAP)

---

Serology samples will be collected at Screening (Visit 1) that assess for presence of human immunodeficiency virus (HIV), hepatitis B surface antigen (HBsAg), and hepatitis C virus (HCV), and will be presented in a subject listing.

Breathalyzer test and urine toxicology results will also be collected at Screening (Visit 1) and Baseline/Dosing [Visit 2 (Day 1)] for all subjects and Visit 7 (Day 45) for Cohorts 1-3 only. The results will be presented in subject listings.

For female subjects, urine/serum pregnancy test results will be collected at for Cohorts 1-3 at Screening (Visit 1), Baseline/Dosing [Visit 2 (Day 1)], Visit 7 (Day 45), and Visit 14 (Day 240) and for Cohort 4 at Screening (Visit 1), Baseline/Dosing [Visit 2 (Day 1)], Visit 8 (Day 45), and Visit 10 (Day 120). Female subjects' reported contraceptive methods and the start date of their last menstrual period at Screening will be presented in a separate subject listing.

Finally, for Cohorts 1-3 only, a hypersensitivity panel will be drawn prior to the first dose on the Baseline/Dosing [Visit 2 Day 1] visit and prior to repeat dose on Visit 7 (Day 45). The sample will be processed if the subject has a hypersensitivity (anaphylaxis or anaphylactoid) reaction. If a hypersensitivity reaction occurs, an additional sample will be collected during the reaction and again after the reaction. A subject listing will display the results of the panel.

Vital signs data, including systolic blood pressure (mmHg), diastolic blood pressure (mmHg), oral temperature (degrees Celsius), and heart rate (BPM) will be summarized continuously by treatment group at Screening, Baseline/Dosing, Visit 3 (24 Hours), and then all subsequent visits and listed by subject and parameter at the aforementioned time points. For subjects who have repeat vital signs measurements within the same visit, the latest measurements will be used for analysis in table summaries and all measurements will be listed.

A 12-lead electrocardiogram (ECG) will be performed for each subject at Screening and for Cohorts 1-3 at Visit 6 (Day 15). Results will be categorized as normal sinus rhythm, normal variant, and abnormal, and summarized categorically using counts and percentages. The table summary will further summarize the number of subjects with a QTc interval greater than 450 milliseconds, with those subjects' QTc values summarized using continuous descriptive statistics for each group. An ECG subject listing will also be displayed.

Abbreviated physical examinations will be conducted for all subjects at Screening and Baseline/Dosing and for Cohorts 1-3 at Visit 14 (Day 240). The examinations will consist of the following tests/parameters: HEENT, Respiratory, Extremities, Neurological, Cardiovascular/Heart, Musculoskeletal, Dermatologic, Pulmonary, Gastrointestinal/Abdominal, Genitourinary, Endocrine, and General Appearance. Results will be summarized categorically [Normal, Abnormal Clinically Significant (CS), Abnormal Not Clinically Significant (NCS), or Not Done] for each test/parameter at each of the three visits. A subject listing will display all physical examination results by time point and test/parameter. Finally, symptom-directed physical examinations will be conducted based on an unsolicited complaint from the subject, whose results will be

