8.4. Electrocardiogram

A 12-lead ECG will be performed at screening (all cohorts) and Day 15 (Cohorts 1-3) and reviewed by the study PI or a co-Investigator to assess the cardiac status of a subjects for enrollment and for any significant changes at Day 15 (Cohorts 1-3). ECGs will be performed after the subject rests quietly for at least 10 minutes. To be eligible for participation, the QT interval should be ≤ 450 ms, and there must be no clinically significant ECG abnormalities according to the study investigators and may be repeated once.

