- Chemistry panel that will include serum creatinine, BUN, calcium, total bilirubin, alkaline phosphatase, ALT, AST, sodium, potassium, albumin, PT, PTT, INR, total CK, carbon dioxide, and chloride. Subjects should be fasting for the chemistry panel.
- A CBC with differential will be obtained including WBC, RBC, hemoglobin, hematocrit, platelet count, MCV, MCH, MCHC, RDW, MPV, neutrophils, lymphocytes, monocytes, eosinophils, and basophils.
- A serum pregnancy test will be obtained at screening for all women of reproductive capacity. A urine pregnancy test will be obtained and must be resulted prior to Day 1 dosing. Results must be confirmed as negative before study product is dosed.
- Urine drug screening.
- A urine dipstick will be done to evaluate for presence of protein, glucose or blood in urine. If dipstick is abnormal (>+1), a complete urinalysis with microscopic will be performed.
- A 12-lead ECG will be done during screening. Subjects with a QTc interval >450 milliseconds will be excluded from participation.
- Viral Serology includes HIV, HBsAg and antibody to HCV.
- Serum from subjects who give consent will be stored for future use.
- The Hypersensitivity Panel includes cytokine and complement panels, IgE, and tryptase. Refer to lab manual for further processing instructions. .
- PK samples will be collected for all subjects at pre-dose, 24 hours and 72 hours post dose, and on Days 8, 15, 45 (before repeat-dose or placebo), 49, 90, and 120.
- Serological samples (PD) will be collected for all subjects at pre-dose, 24 hours post dose, and on Days 8, 15, 45 (before repeat-dose or placebo), 49, 90, and 120.
- ADA samples will be collected and tested for all subjects at pre-dose and Days 15, 45 (before repeat-dose or placebo), 60, 90, 120, 150, 180, and 240.
- Samples to be collected pre-dose prior to Day 45 repeat dose.
- Subjects will be provided a reactivity diary prior to leaving the clinic on baseline/dosing Day 1. Subjects will be asked to complete daily diary records study Day 1-7 and diary is to be collected by site staff on Day 8 for review. Subjects will be provided a reactivity diary prior to leaving the clinic on baseline/dosing Day 45. Subjects will be asked to complete daily diary records study Day 46-52 and diary is to be collected by site staff on Day 60 for review.

Table 3: Schedule of Assessments (Cohort 4)

Study Visit	Screening ¹	Baseline/ Dosing ²		3	4	5	6	7	8	9	10	Unscheduled
		D 1	8-Hour Stay									

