#### 4.2 Data Safety Monitoring Board

A centralized, independent DSMB will be established in collaboration with Resilience Government Services, Inc. and ICON and will oversee the safety conduct the study. The DSMB will make safety and tolerability recommendations.

Following data and documents will be generated for DSMB review:

- Incidences and listings of overall Adverse Events (AEs), Medically Attended Adverse Events (MAAEs), and Serious Adverse Events (SAEs)
- Summaries and listings of change from baseline in electrocardiogram, vital signs, and clinical safety laboratory values
- Other relevant data / documents:
  - Number of enrolled subjects
  - Number of subjects withdrawn and subject dispositions
  - Subject characteristics and anthropometric measures data (including age, height, weight, and BMI)
  - Protocol deviations will be summarized. Listings for Per-Protocol (PP) population will not be available for DSMB meetings and there will not be DSMB analyses based on the PP population.

Blinded tables, figures, and listings (TFLs) will be provided for the open session of DSMB meetings. A dummy randomization schedule will be used to assign the subjects to groups, whereby subjects will be summarized in their true treatment group, but treatment groups will be arbitrarily labeled and ordered in tables to preserve the blind.

Four DSMB meetings are planned for Cohorts 1-3, and one DSMB meeting is planned for Cohort 4.

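### SAP 9.10.2 gives continuous QTc statistics only for subjects above 450 ms, the entry-exclusion level, and plans no ECG change from baseline or shift table for the final analysis

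*SAP*

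**What the plan says.** SAP 9.10.2 covers physical examination, vital signs, ECG and laboratory results. The ECG is "performed for each subject at Screening and for Cohorts 1-3 at Visit 6 (Day 15"), so a post-dose ECG exists only in Cohorts 1-3. Four outputs are planned:

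- a three-level category: "Results will be categorized as normal sinus rhythm, normal variant, and abnormal, and summarized categorically using counts and percentages";
- a count: the table will "further summarize the number of subjects with a QTc interval greater than 450 milliseconds";
- for the subjects in that count only, their "QTc values summarized using continuous descriptive statistics for each group";
- a listing: "An ECG subject listing will also be displayed".

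Three other places bear on this.

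- Protocol Appendix A, Table 2, footnote 11: "Subjects with a QTc interval >450 milliseconds will be excluded from participation". Exclusion criterion 4 is softer, giving repeated readings above 450 ms as its example.
- Protocol 8.4: the investigator reviews the ECG for enrolment and "for any significant changes at Day 15 (Cohorts 1-3").
- SAP 4.2, among the outputs for the safety board: "Summaries and listings of change from baseline in electrocardiogram, vital signs, and clinical safety laboratory values".

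**The concern.** The only continuous QTc summary planned for the final analysis is conditioned on the outcome. A subject contributes a QTc value only after crossing 450 ms, and anyone who crossed it at screening should not have been enrolled. The table uses the Safety population, so screen failures are absent. The screening row is therefore nearly empty by design, apart from a passed repeat or a deviation, and the Day 15 values stand with almost no baseline beside them.

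A mean taken above a cut-off also responds little to a shift of the whole distribution. When everyone moves up a few milliseconds, subjects who were just below the line enter the group at its lower edge and hold the mean down. At stake is whether the final report can describe a modest QTc difference between either dose and placebo, using ECGs taken to look for change.

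**Working it through.** **Step 1. How 9.10.2 treats neighbouring parameters.**

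| Parameter | Continuous summary | Change from baseline | Shift table |
|---|---|---|---|
| Laboratory | all subjects, each time point | yes | yes, for categorical parameters |
| Vital signs | all subjects, each visit | in Table 2 of the SAP and protocol 11.5.3 | not stated |
| ECG (QTc) | only subjects above 450 ms | not stated | not stated |

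SAP 4.2 plans ECG change from baseline, but only for the safety board. The final-analysis section has no counterpart.

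**Step 2. Inputs.** From the documents: the 450 ms cut-off and planned group sizes of 150, 150 and 75. The documents give no QTc mean, SD or target effect, so there is no plan figure to reproduce. Assumed: Day 15 QTc is normal with mean m = 405-415 ms and SD s = 18-20 ms; true shifts are 5, 10 or 20 ms; SD of change is 12-20 ms.

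**Step 3. The mean among subjects above 450 ms.** With z = (450 - m)/s, the share above is P = 1 - Φ(z), and the mean above is m + s·φ(z)/P.

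- m = 410, s = 18, no shift: z = 40/18 = 2.222; P = 0.0131 (about 1 of 75, 2 of 150); mean = 410 + 18 × 0.03377/0.01313 = 456.3 ms.
- Shift of 10 ms: z = 30/18 = 1.667; P = 0.0478 (about 7 of 150); mean = 420 + 18 × 0.09948/0.04779 = 457.5 ms.

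A 10 ms effect thus moves this mean by about 1.2 ms. Over the grid, the smallest movement is 0.5 ms (m = 405, s = 18, shift 5: 455.8 to 456.3). The largest is 1.5 ms (m = 415, s = 20, shift 10: 458.1 to 459.6).

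A simulation that removes subjects above 450 ms at screening agrees. It used screening means of 400-420 ms and between/within-subject SDs of 15/10 or 18/12 ms. A 10 ms shift left a gap of 1.0-1.8 ms.

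**Step 4. The planned count.** The same simulation, one active cohort of 150 against 75 placebo, two-sided 0.05. The power figures only illustrate sensitivity. With no shift, 0.2-3.8 of 75 placebo subjects are expected above 450 ms.

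| True shift | Expected above 450 ms, of 150 active | Power of the count | Power of mean change, all subjects |
|---|---|---|---|
| 5 ms | 0.8-12.7 | 0.03-0.13 | 0.56-0.72 |
| 10 ms | 1.8-19.9 | 0.06-0.50 | about 0.99 or more |
| 20 ms | 6.9-41.0 | 0.40 to about 1.00 | about 1.00 |

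**Step 5. Precision of the alternative.** The 95% half-width for a difference in mean change is 1.96 × SD × √(1/150 + 1/75) = 1.96 × SD × 0.1414. This gives 3.3, 4.2 and 5.5 ms for SDs of 12, 15 and 20 ms. These figures pool the two lots of a dose. For a single lot, 75 against 75, the factor is √(2/75) = 0.1633, and the half-widths for SDs of 12 and 20 ms are 3.8 and 6.4 ms.

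**The case against.** The strongest reply is that the count above 450 ms comes first in the plan and is informative. Because that level excludes at entry, a Day 15 count above it is essentially a count of new exceedances, so a sparse screening row is not in itself a fault. In the worked example a 10 ms effect takes the expected count from about 2 to about 7 of 150. This stands, and the count should be kept. It remains weak for shifts of 5-10 ms.

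Three stronger readings are tempting, and the documents do not support them.

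- *No ECG change from baseline is planned anywhere.* SAP 4.2 plans it for the safety board. The gap is in the final-analysis section. Table templates are in a separate document, but 9.10.2 as written gives them no basis for this summary.
- *A QTc effect would be practically invisible.* A shift of about 20 ms would usually show in the count, and individual results are listed.
- *A primary endpoint is compromised.* ECG is in the heading of 9.10.2, but endpoint 1b as worded names physical examination, vital signs and laboratory values. Protocol 11.5.3 plans no ECG analysis, and no formal hypothesis testing is planned.

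One may also say that protocol 8.4 describes clinical review of individual tracings, which the category, count and listing support. That is fair, but it does not explain why the only continuous summary is confined to the subjects above the cut-off.

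**Conclusion.** The point holds as a limited defect in the analysis plan. The one continuous QTc statistic in 9.10.2 is nearly insensitive to a modest shift: about 0.5-1.5 ms of movement for a true 5-10 ms. A summary of change in all subjects would estimate such a shift to within about 3.3-5.5 ms. The section is also out of step with SAP 4.2 and with the purpose given in protocol 8.4. Every size quoted rests on an assumed QTc distribution and SD of change; the textual mismatch does not. The matter concerns Cohorts 1-3 only, since Cohort 4 has no post-dose ECG. It merits correction because descriptive summaries are the trial's main safety method and the data are in hand.

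**What to change.** In SAP 9.10.2, for Cohorts 1-3:

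- summarise QTc at Screening, at Day 15 and as change from baseline in all Safety subjects with both ECGs, by treatment group including placebo;
- add a Screening-to-Day 15 shift table for the three ECG categories;
- keep the planned count above 450 ms. No further QTc categories are needed, and the restricted summary need not be removed once the all-subject one is added.

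Align this text with SAP 4.2, so that the final report carries the change-from-baseline summary already planned for the safety board. The cost is SAP wording and one revised table. Protocol 3.1.3 says that all subjects in Cohorts 1-3 have completed their last visit, so no further ECG is required.

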## Statistical Analysis Plan (SAP)

---

displayed in a separate listing. Symptom-directed physical examinations can be performed at any visit, scheduled or unscheduled.

Unscheduled visit data for all safety analyses will be presented in listings but not included in table summaries, with the exception that an unscheduled visit result will serve as a subject's baseline result if it is their last result prior to first treatment administration.

All safety analyses will be presented for the Safety population.

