5. INVESTIGATIONAL PLAN

5.1. Study Design

This is a Phase 2, multicenter, randomized, double-blinded, placebo-controlled study to evaluate the safety, tolerability, pharmacodynamics (PD), and immunogenicity of a single dose (100 mg) and a repeat dose (50 mg and 100 mg) of G03-52-01 administered by IM injection(s) in adult subjects ([Appendix C](#)).

Approximately 625 subjects will be enrolled in this study to receive active product or placebo on Day 1 or Day 1 and Day 45, and will be randomized to the following concurrent cohorts:

- Cohort 1 (N=150, 75 lot #1, 75 lot #2): 50-mg dose
- Cohort 2 (N=150, 75 lot#1, 75 lot#2): 100-mg dose
- Cohort 3 (N=75): Placebo
- Cohort 4 (N=250): 100 mg dose or Placebo

The study will include up to 14-day screening period and an approximately 1-hour stay for Cohorts 1-3 and 8 hours stay for Cohort 4 in the clinic after dosing is complete for PK assessment and to ensure that no hypersensitivities or safety signals occur. Follow-up visits will occur at 24 hours and 72 hours post dose, and on Days 8, 15, 45, 49, 60, 90, 120, 150, 180, and 240 for Cohorts 1-3. For Cohort 4, follow-up visits will occur 24 hours, 72 hours, and on Days 8, 15, 30, 45, 90, and 120.

Safety Analysis

Safety labs will be drawn at pre-dose, 24 hours post dose, and on Days 15, 45 (before repeat-dose or placebo), 60, 120, and 240 for Cohort 1-3. Subjects in Cohort 4 will have safety labs drawn at screening and on Day 15, 45, and 120.

PD Analysis

PD samples will be collected for all subjects. Analysis will be completed by the Battelle Mouse Neutralization Assay (MNA) for Serotypes A and B.

Samples for subjects in Cohorts 1-3 will be tested at pre-dose, 24 hours post dose, and on Days 8, 15, 45 (before repeat-dose or placebo), 49, 90, and 120. The first 25 subjects randomized for each DP lot of 50 mg and 100 mg doses and placebo will be tested at all 8 timepoints. The remaining samples from the subjects who received either dose or lot of G03-52-01 (including placebo) will only be tested using MNA at pre-dose and Days 45, 90, and 120.

All subjects in Cohort 4 will have samples collected at pre-dose, 2 hours, 4 hours, 8 hours, 24 hours and on Days 30, 45, and 90. Samples will be analyzed for the first 30 subjects in Cohort 4, who receive active drug and complete the sample collection at 24 hours. See [Figure 2](#) and [Figure 3](#).

PK Analysis

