9.4. Unscheduled visits

A subject may return to the clinic for an unscheduled visit at any time. The following activities at a minimum should be performed:

- Obtain vital signs
- Perform symptom-directed PE as appropriate
- Review and update concomitant medications
- Assessment of AEs and SAEs

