11.5.3. Safety and Tolerability

All safety analyses will be based on the safety population, unless otherwise stated.

AEs will be coded using Medical Dictionary for Regulatory Activities® (MedDRA® Version 24.0). All AEs that occur after the initiation of study medication will be summarized using frequency counts and percentages. Summaries will be presented by treatment group. The following summaries will be presented for AEs and SAEs:

- Overall (i.e., regardless of severity or relationship to treatment)
- By severity grade (mild, moderate, or severe)
- By relationship to study medication
- By MedDRA® level hierarchy (system organ class and preferred term)

Unless otherwise specified, at each level of subject summarization in reporting the incidence of an AE, a subject will only be counted once if the subject reported one or more occurrence of an event. If more than one occurrence of an event is reported, the event of the worst severity or the worst-case relationship assessment will be summarized.

Vital signs (HR, BP, respiratory rate, pulse oximetry and body temperature), PEs, and clinical laboratory values, including change from baseline, will be summarized descriptively by treatment group, including both visit values and change from baseline (measured at admission) to each visit. In addition, shift tables, showing individual subject changes from baseline will be presented for laboratory parameters using toxicity grading. Subjects with graded values of vital

sign and laboratory parameters will be identified in listings, along with significant changes identified in the symptom-directed physical examinations.

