### 9 Statistical Methods

#### 9.1 General Statistical Conventions

All statistical procedures will be completed using SAS version 9.4 or higher.

Unless otherwise stated, all statistical testing will be two-sided and will be performed using a significance (alpha) of 0.05. Two-sided 95% confidence intervals (CI) will be provided where relevant.

Continuous variables will be summarized using descriptive statistics, including number of subjects (n), mean, median, standard deviation (SD), first quartile (Q1), third quartile (Q3), minimum, and maximum. Means, medians, and quartiles (if averaged value) will be rounded to one more decimal place than what is reported in the data. SDs will be rounded to two more decimal places than what is reported in the data.

For categorical variables, summaries will include counts of subjects and percentages. Percentages will be rounded to one decimal place.

For summary purposes, baseline is defined as the last measurement prior to the first treatment administration. All summaries will be presented by treatment group and for all subjects, unless otherwise specified.

All subject data, including those derived, will be presented in individual subject data listings. Unless otherwise stated, unscheduled visit results will be included in date/time chronological order within subject listings. All listings will be stratified by treatment group and sorted by subject ID in ascending numerical order, and date/time in ascending chronological order. The subject's race, sex, and age will be stated on each listing. Unless otherwise stated, data listings will be based on all randomized subjects (ITT Population).

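### The maximum-shift laboratory table leaves out post-dose unscheduled results, so it can understate, but never overstate, a subject's worst shift

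*SAP*

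**What the plan says.** SAP 9.10.2 covers changes from baseline in examination, vital signs and laboratory values. For the laboratory shift tables it says: "Shift tables will include both the shift from baseline to each post-baseline visit as well as the maximum shift from baseline". The Protocol, section 11.5.3, sets the scale: "shift tables, showing individual subject changes from baseline will be presented for laboratory parameters using toxicity grading".

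Near the end of SAP 9.10.2 a general rule follows: "Unscheduled visit data for all safety analyses will be presented in listings but not included in table summaries". The same sentence makes one exception: "an unscheduled visit result will serve as a subject's baseline result if it is their last result prior to first treatment administration". SAP 9.1 adds that "unscheduled visit results will be included in date/time chronological order within subject listings".

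Protocol 5.1 gives the laboratory schedule. For Cohorts 1-3: "Safety labs will be drawn at pre-dose, 24 hours post dose, and on Days 15, 45 (before repeat-dose or placebo), 60, 120, and 240". The schedule in Cohort 4 is sparser: "Subjects in Cohort 4 will have safety labs drawn at screening and on Day 15, 45, and 120". Protocol 9.4 allows visits between these times: "A subject may return to the clinic for an unscheduled visit at any time". Its minimum activities for such a visit do not include laboratory tests. Protocol 11.5.3 says nothing about how unscheduled results enter the shift tables.

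**The concern.** Restricting by-visit summaries to scheduled visits is sound practice, because it keeps the time points comparable. A maximum-shift table has a different purpose. It reports how far each subject moved at worst after dosing, and a reader will take it to cover all post-dose data. Under the SAP rule, an unscheduled result can set a subject's baseline but can never set the subject's worst post-dose value.

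Primary endpoint 1b, as worded in Protocol 4.2.1, is the occurrence of changes from administration to the final follow-up visit. It is not limited to scheduled samples. At stake is whether the one summary of worst laboratory change matches the subject listings, and whether a graded abnormality found between visits is counted in any laboratory table.

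**Working it through.** The plan gives no figure to reproduce. The check sets the texts side by side, then looks at the schedule, then gives a conditional illustration.

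**1. Scope of the rule.** The exclusion covers table summaries for all safety analyses. The maximum-shift table is a table summary within a safety analysis. The single exception concerns a result before first dosing, which cannot be a post-dose worst value. Nothing else in SAP 9.1 or 9.10.2 exempts the maximum-shift table.

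**2. Direction of the error.** Let S be a subject's scheduled post-dose grades and U the unscheduled ones. Then max(S) ≤ max(S and U together). The tabulated worst grade equals the true worst grade or is lower. It is lower exactly when some grade in U is higher than every grade in S. In a hypothetical case, a Cohort 4 subject is ungraded at baseline and on Days 15, 45 and 120, with a valid Grade 3 result at an unscheduled visit between Days 45 and 120. The table shows no shift, while the listing shows Grade 3.

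**3. Schedule (Protocol 5.1).**

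| | Scheduled post-dose laboratory times | Number | Gaps in days, from Day 1 |
|---|---|---|---|
| Cohorts 1-3 | 24 h (Day 2), Days 15, 45, 60, 120, 240 | 6 | 1, 13, 30, 15, 60, 120 |
| Cohort 4 | Days 15, 45, 120 | 3 | 14, 30, 75 |

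The Cohort 4 visits at 24 hours, 72 hours and Day 8 (Protocol 9.2.3 to 9.2.5) include no safety laboratory tests. A change in Cohort 4 that arises and resolves before Day 15 can be seen only in an unscheduled sample.

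**4. Illustration, given that an unscheduled result exists.** These are assumptions, not trial data. With s scheduled and u unscheduled values that are exchangeable and continuous, P(the highest is unscheduled) = u/(s + u).

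- u = 1: 1/(6 + 1) = 14.3% in Cohorts 1-3; 1/(3 + 1) = 25.0% in Cohort 4.
- u = 2: 2/(6 + 2) = 25.0%; 2/(3 + 2) = 40.0%.

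A simulation of independent normal values (300,000 per setting) raised the mean of one unscheduled value:

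| Mean raised by | Cohorts 1-3 | Cohort 4 |
|---|---|---|
| 0.5 SD | about 26% | about 39% |
| 1 SD | about 41% | about 55% |
| 2 SD | about 73% | about 82% |

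These are probabilities that the unscheduled value is the highest. The shift category changes only if that value also crosses a grade boundary, so under the same assumptions each figure is an upper limit on the chance of a changed category. The illustration says nothing about how many subjects have an unscheduled laboratory test.

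**The case against.** The strongest case against has four parts.

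**The values are not lost.** The laboratory listings show the result, change from baseline, normal range and clinical significance, and unscheduled results are listed. An abnormal laboratory finding can be an adverse event (Protocol 9.8.1), and one that leads to a medical encounter can be a medically-attended event (Protocol 9.8.4). Such events are tabulated by maximum severity. This stands, but only in part: a graded value that the investigator does not report as an adverse event reaches no table, and AE tables do not show shift from baseline.

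**Unscheduled laboratory tests may be few.** They are not among the minimum activities at an unscheduled visit. This stands, and it limits frequency. It does not change what the rule does when a sample is taken.

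**Unscheduled values need not be the worst.** A reader might infer that such samples are drawn because something looks wrong, so that the rule removes the most extreme values. The documents do not say why these samples are drawn. One that follows up an abnormal scheduled result may be closer to normal, and the scheduled abnormality is then already in the table. Only a new peak is missed.

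**The rule treats all arms alike, and including every draw has its own cost.** Subjects with more samples have more chances of an extreme value, and Protocol 8.5.2 recognises laboratory error as a reason for a repeat. Both points are fair and shape the fix. Equal treatment of the arms does not make a maximum complete.

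**Conclusion.** The point holds on the text. As written, the maximum-shift table reflects scheduled visits only and can err in one direction, towards too small a shift. The size is unknown, because the documents give neither the number of unscheduled laboratory samples nor the reasons for them. The effect is most plausible in Cohort 4, with three scheduled post-dose laboratory times in 120 days.

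The documents do not support two stronger readings. A reader might infer that unscheduled results are barred from every table; in fact, a pre-dose one can enter as baseline. A reader might also assume a rate, say 1-5% of the 200 active Cohort 4 subjects, and conclude that 2-10 subjects (0.01 × 200 to 0.05 × 200) are placed in too low a category. The documents give no basis for that rate, and a peak that stays within the same grade moves nobody.

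The conclusion assumes that the exclusion is programmed as written and that some unscheduled laboratory samples are taken after dosing. It is worth correcting because it concerns a summary for a primary safety endpoint and the correction is small.

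**What to change.** Amend SAP 9.10.2 to say that by-visit summaries and by-visit shifts use scheduled visits only, while the maximum-shift table uses all valid post-dose results, scheduled and unscheduled, excluding results documented as laboratory error. Keep the existing baseline exception.

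The cost is one sentence and one changed derivation, with no new data collection. The downside is that subjects with more samples have a slightly higher chance of an extreme value; a footnote to the table can say so. If the SAP can no longer be amended, SAP section 1 provides for deviations to be described and justified in the study report, and the change can be made there.
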